6.2.4 Stopping Rules for Investigational Product

For safety purposes, smoking should be temporarily stopped in the event of any signs suggesting nicotine overexposure, (e.g., gastrointestinal disturbance [nausea, vomiting, diarrhea, stomach or abdominal pain], cold sweats, headache, dizziness, and breathing problems) or any reasons at the discretion of the Investigator or designee.

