**Table 10: Categorical Variables Definitions**

Variable	Categories
BMI (kg/m ²)	Underweight: < 18.5 Normal range: ≥ 18.5 and < 25.0 Overweight: ≥ 25.0 and < 30.0 Obese: ≥ 30.0
FTND total score	Mild: 0 - 3 Moderate: 4 - 6 Severe: 7 - 10
Daily CC consumption over the last 4 weeks as reported at Screening (per day).	10-19 >19
CO breath test level (ppm)	≤ 10 > 10
COHb level	≤ 2% > 2%
Adverse event severity	Mild Moderate Severe
Adverse event relationship	Related Not related
Adverse event expectedness	No Yes
Action taken with study product due to adverse event	Product use interrupted Product use stopped Product use reduced Not applicable None
Outcome of adverse event	Death related to adverse event Not recovered or not resolved Recovered or resolved Recovered or resolved with sequelae Recovering or resolving Unknown
Seriousness Criteria	Fatal Life-threatening Requires hospitalization Results in disability/incapacity Congenital anomaly/birth defect
Severity of device event	Major Minor

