12.6.4.2 Adverse Events

12.6.4.2.1 All Adverse Events

All AE tables will be presented by randomized arm.

A general summary table of AEs will be presented including:

- The number of events and the number and percentage of subjects reporting at least one AE.

- The number of events and the number and percentage of subjects reporting at least one study product –related AE, broken down by product relatedness (related to THS 2.2 / CC) and expectedness (expected for THS 2.2 / CC).
- The number of events and the number and percentage of subjects reporting at least one AE broken down by severity including each subject only once with his worst severity.
- The number of events and the number and percentage of subjects reporting at least one SAE.
- The number of events and the number and percentage of subjects reporting at least one AE leading to any action taken, broken down by action taken related to the product (product use interrupted, product use reduced, product use stopped, not applicable, none), treatment given (yes, no), study discontinuation, other action taken.
- The number of events and the number and percentage of subjects reporting at least one AE related to study procedure

Additional summary tables of AEs will be presented with a breakdown of the number of events, as well as the number and percentage of subjects reporting each AE, categorized by system organ class (SOC) and preferred term (PT) coded according to the Medical Dictionary for Regulatory Activities (MedDRA) dictionary (version 16.0):

- The number of events and the number and percentage of subjects reporting at least one AE.
- The number of events and the number and percentage of subjects with at least one AE related to product exposure and expectedness for investigational product (IP; THS 2.2 or CC).
- The number of events and the number and percentage of subjects with at least one AE leading to product discontinuation or reduction.
- The number of events and the number and percentage of subjects with at least one AE leading to study discontinuation.
- The number of events and the number and percentage of subjects with at least one AE related to study procedure.
- The number of events and the number and percentage of subjects with at least one AE by severity (mild, moderate, severe).

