If a subject has more than one occurrence of the same AE, the subject will be counted only once within a PT with the worst occurrence based on the presentation (e.g., for presentation by severity = most severe, for presentation by relationship = most related). Missing information on the intensity of AE will be counted as severe.

The data will be presented in the below outputs, the TFL number refers to the TFL number in the accompanying TFL shell document:

TFL number	Title
TABLES	
15.2.6.1	Summary of Adverse Events – Safety Population
15.2.6.2.1	Summary of Adverse Events by System Organ Class and Preferred Term – Safety Population
15.2.6.2.2	Summary of Adverse Events by System Organ Class – Safety Population
15.2.6.2.3	Summary of Adverse Events by Preferred Term – Safety Population
15.2.6.3	Summary of Adverse Events by System Organ Class, Preferred Term and Relationship to Study Product Exposure for Investigational Product (THS 2.2 or CC) and Expectedness – Safety Population
15.2.6.4	Summary of Adverse Events Leading to Investigational Product (THS 2.2 or CC) Discontinuation or Reduction by System Organ Class and Preferred Term – Safety Population
15.2.6.5	Summary of Adverse Events Leading to Study Discontinuation by System Organ Class and Preferred Term – Safety Population
15.2.6.6	Summary of Adverse Events Related to Study Procedure by System Organ Class and Preferred Term – Safety Population
15.2.6.7	Summary of Adverse Events by System Organ Class, Preferred Term and Severity – Safety Population
15.2.6.8	Summary of Serious Adverse Events – Safety Population
LISTINGS	
15.3.6.1.1	Listing of Adverse Events

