13.2 Safety Reporting

Statistical summaries required for safety reporting will be made available to PMI medical safety officer following database lock. The TFLs are listed in the table below.

TFL no.	Title
TABLES	
15.2.1.4.1	Summary of Demographics and Other Baseline Characteristics – Safety Population
15.2.1.4.2	Summary of Demographics and Other Baseline Characteristics – FAS
15.2.1.4.2.1	Summary of Demographics and Other Baseline Characteristics by Sex – FAS
15.2.1.4.2.2	Summary of Demographics and Other Baseline Characteristics by Cigarette Consumption – FAS
15.2.2.1	Summary of Use of THS 2.2 Product and CC – Safety Population
15.2.6.1	Summary of Adverse Events – Safety Population
15.2.6.2.1	Summary of Adverse Events by System Organ Class and Preferred Term – Safety Population
15.2.6.3	Summary of Adverse Events by System Organ Class, Preferred Term and Relationship to Study Product Exposure and Expectedness – Safety Population
15.2.6.4	Summary of Adverse Events Leading to Study Product Discontinuation or Reduction by System Organ Class and Preferred Term – Safety Population
15.2.6.5	Summary of Adverse Events Leading to Study Discontinuation by System Organ Class and Preferred Term – Safety Population
15.2.6.6	Summary of Adverse Events Related to Study Procedure by System Organ Class and Preferred Term – Safety Population
15.2.6.7	Summary of Adverse Events by System Organ Class, Preferred Term and Severity – Safety Population
15.2.6.8	Summary of Serious Adverse Events – Safety Population
15.2.6.9	Summary of THS 2.2 Device Events – Safety Population
15.2.6.9	Summary of THS 2.2 Device Events – Safety Population

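### No planned table shows which adverse event terms led to interruption of product use, although a temporary stop is the product action that Protocol 6.2.4 directs (minor reporting gap)

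*SAP*

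**What the plan says.** Protocol 6.2.4, the section on stopping rules for the product, gives one instruction: "For safety purposes, smoking should be temporarily stopped in the event of any signs suggesting nicotine overexposure". It then gives examples of such signs, among them nausea, vomiting, headache and dizziness, and adds a second trigger: "or any reasons at the discretion of the Investigator or designee". Either way the action is a temporary stop.

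SAP Table 10 lists the possible product actions after an AE as "Product use interrupted Product use stopped Product use reduced Not applicable None". Interrupted, stopped and reduced are three different values.

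SAP 12.6.4.2.1 uses these values in two ways:
- The general AE summary (Table 15.2.6.1) breaks AEs down by every product action, interruption included, but without event terms.
- The list of tables by SOC and PT has one item that depends on product action: "The number of events and the number and percentage of subjects with at least one AE leading to product discontinuation or reduction". The output is Table 15.2.6.4, titled as a summary of "Adverse Events Leading to Investigational Product (THS 2.2 or CC) Discontinuation or Reduction by System Organ Class and Preferred Term".

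The safety reporting package (SAP 13.2) lists the same table as "Adverse Events Leading to Study Product Discontinuation or Reduction by System Organ Class and Preferred Term", and the topline package (SAP 13.3) repeats that scope.

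**The concern.** The one product action that the protocol tells sites to take appears to be the one with no breakdown by event term. Product is handed out one unit at a time for ad libitum use over 5 days, so a short pause is the natural response to dizziness or nausea. Table 15.2.6.4 could then be empty in both product arms although the stopping rule had been applied several times. Someone reading that table alone, in the safety or topline package, could conclude that no AE affected product use. The documents also give no reason why the general summary names three actions and the SOC/PT item only two. SAP Section 9, on changes from the protocol, does not mention it.

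**Working it through.** There is no planned figure to reproduce. The check traces an AE whose only product action is a temporary stop under Protocol 6.2.4.

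**Step 1: coding.** Table 10 offers interrupted, stopped and reduced. With interrupted available as a separate value, a temporary stop fits it best. This is an inference, because neither document states the coding rule.

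**Step 2: where the AE is counted under that coding.**

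| Output | Event term shown? | Product action shown? | AE counted? |
|---|---|---|---|
| 15.2.6.1 general summary | No | Yes, interruption has its own line | Yes |
| 15.2.6.2.1 all AEs by SOC and PT | Yes | No | Yes |
| 15.2.6.3 by SOC, PT, relationship and expectedness | Yes | No | Yes |
| 15.2.6.4 by SOC and PT, discontinuation or reduction | Yes | Yes, but not interruption | No |
| 15.3.6.1.1 AE listing | Listing of individual AEs | Available in the AE data | Yes |

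The first four outputs are all in both the 13.2 and the 13.3 lists. No table combines event term with interruption.

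**Step 3: an illustration with assumed counts.** The documents give no expected number of interruptions. Suppose k of 80 THS 2.2 subjects and 0 of 40 CC subjects interrupt use because of an AE, and none of them also stops or reduces:
- k = 1: 1/80 = 1.25%
- k = 4: 4/80 = 5%
- k = 8: 8/80 = 10%

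Table 15.2.6.1 shows k versus 0 each time. Table 15.2.6.4 shows 0 versus 0 whatever k is.

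**Step 4: can the missing breakdown be recovered from the other tables?** Not in general. Take k = 4, and let d be the number of THS 2.2 subjects with dizziness in Table 15.2.6.2.1. The number who interrupted because of dizziness can be anything from 0 to the smaller of 4 and d, as long as other terms could account for the rest. Only the individual AE records settle it.

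**Step 5: exceptions.** An AE that led first to interruption and later to a stop or reduction could still enter Table 15.2.6.4. The withdrawal criteria in Protocol 5.1.3 concern leaving the study, not pausing the product, and do not change the mapping.

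**The case against.** The strongest reply is that nothing is hidden. Interruptions are counted by arm in Table 15.2.6.1, and the events are tabulated by term and arm in Tables 15.2.6.2.1 and 15.2.6.3, next to 15.2.6.4 in both packages. In the k = 4 example the reader sees 4 of 80 versus 0 of 40 interrupted. Whether dizziness or nausea was more frequent with THS 2.2 than with CC can be read from the all-AE tables. The daily MCEQ adds items on both symptoms, and its Aversion subscale is compared between these arms with a 95% CI (SAP 12.6.3.1.2). Table 15.2.6.4 also states its own scope in its title. All of this stands, and it limits the point to one missing cross-tabulation.

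Three further replies stand in part:
- The coding is inferred. Protocol 6.2.4 speaks of a temporary stop, Table 10 defines neither interrupted nor stopped, and the SAP does not define discontinuation. The sponsor could say that it includes interruption. The separate values in Table 10 make that the less natural reading, and an undefined term is itself a reason to clarify.
- SAP Section 3 places the detailed table descriptions in a separate shell document, which may define the scope of 15.2.6.4 more fully. That document is not available here.
- The rule also covers investigator discretion, so an interruption cannot be equated with nicotine overexposure.

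**Conclusion.** The point holds as a minor reporting gap. On the natural reading of Table 10, AEs managed only by a temporary stop do not appear in Table 15.2.6.4, and no planned table shows by arm which event terms led to interruption.

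A reader might go further and infer that AEs triggering the stopping rule drop out of AE reporting, or that a difference between THS 2.2 and CC in dizziness or nausea would go unseen. The documents do not support this: the events, their terms and the number of interruptions are all tabulated by arm, and only the link between term and interruption is left to the individual records.

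The conclusion assumes that sites code a temporary stop as interrupted, that discontinuation does not include it, and that the table shells do not say otherwise. How many AEs are concerned cannot be known from the documents; the 1.25% to 10% range is illustrative. The primary analysis, the sample size and every between-arm inference are untouched. The relevance is to the secondary objective of monitoring safety.

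**What to change.** Define Table 15.2.6.4 as AEs leading to product interruption, reduction or discontinuation, by SOC and PT, with a separate column for each action within arm. Use the same scope in four places: the bullet and the output title in SAP 12.6.4.2.1, and the output lists in 13.2 and 13.3. Bring the table shell into line. State in one sentence next to Table 10 that a temporary stop under Protocol 6.2.4 is coded as interrupted, if that is the intention, and say what discontinuation covers.

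The cost is a few words in the SAP and one more value of an existing variable in an existing program. No new data are needed. Protocol 6.2.4 stays as written; only the reporting is aligned with it.

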12.6.4.2.2 Serious Adverse Events (Including Deaths)

A general summary table of SAEs will be presented using the same approach of AEs (see Section 12.6.4.2 “Adverse Events”), and including the number of events and the number and percentage of subjects reporting at least one SAE broken down by seriousness criteria (fatal, life-threatening, requires hospitalization, results in disability/incapacity, congenital anomaly/birth defect).

SAEs will also be listed in a separate listing by actual exposure.

The data will be presented in the below outputs, the TFL number refers to the TFL number in the accompanying TFL shell document:

TFL number	Title
TABLES	
15.2.6.8	Summary of Serious Adverse Events – Safety Population
15.2.6.9	Summary of Serious Adverse Events by System Organ Class and Preferred Term – Safety Population
LISTINGS	
15.3.6.1.2	Listing of Serious Adverse Events

12.6.4.2.3 Adverse Events Leading to Discontinuation

Summaries will be presented for AEs leading to withdrawal, by actual exposure as described in Section 12.6.4.2 “Adverse Events”,

AEs leading to withdrawal will also be listed in a separate listing by actual exposure.

The data will be presented in the below outputs, the TFL number refers to the TFL number in the accompanying TFL shell document:

TFL number	Title
<hr/>	
TABLES	
15.2.6.5	Summary of Adverse Events Leading to Study Discontinuation by System Organ Class and Preferred Term – Safety Population
<hr/>	
LISTINGS	
15.3.6.1.3	Listing of Adverse Events Leading to Study Discontinuation

12.6.4.2.4 Laboratory Abnormalities

Laboratory abnormality data will be listed ordered by actual exposure, subject, parameter and time point. Details related to the toxicity grading of laboratory abnormalities are available in Section 12.6.4.4 “Clinical Laboratory Evaluation”.

The data will be presented in the below outputs, the TFL number refers to the TFL number in the accompanying TFL shell document:

TFL number	Title
<hr/>	
LISTINGS	
15.3.6.4	Listing of Clinical Chemistry Data, Shift, Changes from Baseline and CTCAE grades
15.3.6.5	Listing of Hematology Data Shift, Changes from Baseline and CTCAE grades
15.3.6.6	Listing of Urinalysis Data Shift, Changes from Baseline and CTCAE grades

12.6.4.3 THS 2.2 Device Events

All events relating to the device type will be listed for each subject, including event description, device type the event relates to, severity of event, AE relationship, proposed solution and onset/stop dates/times. Device events will be classified according to [C54451/Medical_Device_Problem_Codes_FDA_CDRH](#)

A summary table of device events will be presented by actual exposure, including:

- Number of device events and the number and percentage of subjects reporting at least one device event.

- Number of device events and the number and percentage of subjects categorized by severity of device event (minor, major)
- Number of device events and the number and percentage of subjects categorized by AE relationship (related, not related)
- Number of device events and the number and percentage of subjects categorized by event description (Cigarette Holder (CH) stops heating, CH does not charge, CH led blinking red, Smoking experience does not start, electronic malfunction, other)

Device events and inventory will be listed by actual exposure. Data collected during Screening will be listed but not summarized.

The data will be presented in the below outputs, the TFL number refers to the TFL number in the accompanying TFL shell document:

TFL number	Title
TABLES	
15.2.6.9	Summary of THS 2.2 Device Events and Malfunctions – Safety Population
LISTINGS	
15.3.6.2	Listing of THS 2.2 Device Events and Malfunctions

12.6.4.4 Clinical Laboratory Evaluation

Table 20 below lists the hematology, clinical chemistry and urine analysis parameters to be assessed in this study.

Table 20: List of Laboratory Safety Parameters

Hematology	Clinical chemistry	Urine analysis
Haematocrit	Albumin	pH
Haemoglobin	Total protein	Bilirubin
Mean corpuscular haemoglobin	Alkaline phosphatase	Glucose
Mean corpuscular haemoglobin concentration	Alanine aminotransferase	Nitrite
Mean corpuscular volume	Aspartate aminotransferase	Red blood cell traces
Platelet count	Blood urea nitrogen	Protein
Red blood cell count	Creatinine	Specific gravity
White blood cell (WBC) count	Gamma-glutamyltransferase	
Differential WBC count:	Fasting glucose	
• Neutrophils	Lactate dehydrogenase	
• Basophils	Potassium	
• Eosinophils	Sodium	
• Lymphocytes	Total bilirubin	
• Monocytes	Direct bilirubin	
	Total cholesterol	
	Triglycerides	

Any clinical safety laboratory test result that is outside of the normal reference range will be reviewed by the PI and assessed for clinical relevance. If the PI considers the abnormal result to be of clinical relevance, then it must be recorded as a concomitant disease at Screening, or if not present at Screening, as an AE during the study. If the condition worsens from screening to after product-use it will be recorded as an AE.

The grading scheme used in the Common Terminology Criteria for Adverse Events and Common Toxicity Criteria [CTCAE] version 4.03) will be used by the PI to assess abnormal laboratory AEs. These CTCAE grades will be derived programmatically in the creation of the datasets.

Laboratory data will be summarized and listed at Screening, Day 0 and at Day of Discharge (Day 6 or day of withdrawal), together with changes from baseline. The number and percentage of subjects with normal results, high/low results and abnormal clinical result (as defined by PI comment) will be tabulated for laboratory parameters.

Listings for the clinical laboratory data will include the following information: normal/ high/low (with respect to the reference range), abnormal clinically relevant (as defined by the PI comments), the PI comments, the change from baseline and the CTCAE grade. Only CTCAE grades greater than zero will be presented

The data will be presented in the below outputs, the TFL number refers to the TFL number in the accompanying TFL shell document:

TFL number	Title
TABLES	
15.2.6.12	Summary of Clinical Chemistry Parameters – Safety Population
15.2.6.13	Summary of Hematology Parameters – Safety Population
15.2.6.14	Summary of Urinalysis Parameters – Safety Population
LISTINGS	
15.3.6.4	Listing of Clinical Chemistry Data, Shift, Changes from Baseline and CTCAE grades
15.3.6.5	Listing of Hematology Data Shift, Changes from Baseline and CTCAE grades
15.3.6.6	Listing of Urinalysis Data Shift, Changes from Baseline and CTCAE grades

12.6.4.5 Vital Signs, Physical Findings and Other Observations Related to Safety

12.6.4.5.1 Prior and Concomitant Medication

Prior medication is defined as any medication that started and ended prior to Screening. Concomitant medication is defined as any medication starting on or after Screening. Medications that started prior to Screening and are ongoing at Screening are considered as concomitant.

All medications will be listed by actual exposure using PT and Anatomical Therapeutic and Chemical (ATC) codes (World Health Organisation-Drug Dictionary Enhanced [WHO-DDE] Q1 2012). A flag will be presented on the listing indicating whether the medication is prior or concomitant. Partial dates will not be imputed, but assumptions will be made as follows to assign to either prior or concomitant:

Date information	Assign as
Missing stop date	Concomitant
Partial date, e.g. --May2012, or ----2011. If month/year is the same as, or later than the month and/or year of Screening.	Concomitant
Partial date, e.g. --May2012, or ----2011. If month and/or year is earlier than the month and/or year of Screening.	Prior

Prior and concomitant medications will be listed by actual exposure. Concomitant medications will be summarized for the Safety Population showing the number (%) of subjects who used the medication at least once by actual exposure and by ATC 1st and 2nd levels and preferred drug name. Listings will be provided by arm and will display original dates (no imputation).

The data will be presented in the below outputs, the TFL number refers to the TFL number in the accompanying TFL shell document:

TFL number	Title
TABLES	
15.2.6.10.1	Summary of Prior Medication by Anatomical Therapeutic Classes (ATC) 1 and 2 – Safety Population
15.2.6.10.2	Summary of Prior Medication by Preferred Drug Name – Safety Population
15.2.6.11.1	Summary of Concomitant Medication by Anatomical Therapeutic Classes (ATC) 1 and 2 – Safety Population
15.2.6.11.2	Summary of Concomitant Medication by Preferred Drug Name – Safety Population
LISTINGS	
15.3.6.3	Listing of Prior and Concomitant Medication

12.6.4.5.2 Physical Examination

Physical examination data recorded at the Screening visit, Admission (Day -2) and at the day of Discharge (Day 6 or at the day of withdrawal for withdrawn subjects) will be listed by actual exposure. Subject's data with abnormal and abnormal clinically significant physical examination findings will be flagged. The number of subjects (%) with normal, abnormal and abnormal clinically significant results will be tabulated by body systems at Screening, Admission and day of Discharge.

Body weight recorded at Admission and day of Discharge; and body height recorded at the Screening visit will also be listed together with BMI. Descriptive statistics of body weight, body height and BMI (BMI will also be categorized as shown in Section 7.5 “Categorical Variables”), at Admission and Day of Discharge will be presented.

The data will be presented in the below outputs, the TFL number refers to the TFL number in the accompanying TFL shell document:

TFL number	Title
TABLES	
15.2.6.18	Summary of Weight and BMI Measurements – Safety Population
LISTINGS	
15.3.6.10	Listing of Physical Examination Findings, Shift and Changes from Baseline

